14.1. Screening assessment domains

We will assess the following by self-report:

1. Age
2. Able to conduct activities in English or Spanish
3. African American or Black and/or Latino or Hispanic race/ethnicity
4. Residence in the NYC
5. In the past month, was employed as a frontline worker in an essential occupation listed in this protocol
6. Has a phone that can be used for study participation and can receive TMs (in the event the participant is assigned to Component B)
7. Has not been fully vaccinated for COVID-19 (we will ask to see vaccine certificates if available but this is not required and those who have not received any dose of a vaccine will not have a certificate)

8. Has not been tested for COVID-19 in the past six months
9. If previously diagnosed with COVID-19, has not been symptomatic in the past two weeks or 90 days has passed since treatment with monoclonal antibodies or convalescent plasma
10. Has not been educated/interviewed as a peer for Component C
11. Willing to engage in a core session and be randomly assigned to receive 1-4 components
12. Not a Community Advisory Board member
13. Willing to follow NYU's COVID-19 guidelines (e.g., complete daily screener, facial coverings, social distancing)
14. Willing to provide locator information

14.1.1. Domains in the assessment battery (BL and FU), Table 4

We will use the Common Data Elements developed by the RADx-UP group for the majority of domains described in Table 4.

Table 4. Description of the measures in the assessment battery (RADx-UP Common Data Elements will be used)

Moderating influences	
Screening CDE	Identity, Age, race/ethnicity, sex assigned at birth, preferred language (CDE), ZIP code of residence, essential worker (Are you considered an essential worker? An essential worker is someone who was required to go to work even when stay at home orders were in place.)
Socio-demographics, background factors	sexual orientation, gender identity, immigration status, racism and discrimination experiences, ¹⁰³
	Health status - CDE
	Highest level of education – CDE
	Housing Employment and Insurance - CDEs
	Effects of COVID - CDEs
	Family income – CDE
	Past COVID-19 testing - CDE
	Medical History - CDE
Other CDEs	
Alcohol and tobacco	Alcohol and tobacco
	Work PPE and Distancing
Individual/attitudinal influences	
Knowledge	8-item true-false questionnaire on aspects of COVID-19 ¹⁰⁴

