14.4. Secondary outcome evaluation

Secondary outcomes include:

- Result of each COVID test
- If diagnosed with or has a positive COVID test result
 - confirmatory testing, as needed (PCR testing is recommended for symptomatic negative and asymptomatic positive persons who carry out a rapid test)
 - contact tracing
 - self-isolation
 - health care receipt
 - unintended consequences

For all participants:

- attitudes toward COVID-19 vaccination
- receipt of COVID-19 vaccination (the CDC vaccination card will be shown if possible)

These primary and secondary outcomes will be examined in mixed methods and integrated analyses.

15. Statistical Considerations

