15.1. Sample size, precision, and statistical power

For the primary outcome, COVID-19 testing by the final follow-up, we used PASS 2021¹³⁹ to estimate the sample size needed for individual main effects of intervention components corresponding to odds ratios of 2.0 in logistic regression, given $\alpha=.05$. Assuming participants not receiving or receiving the lowest intensity of each component have a 20% chance of testing by the final follow-up, a sample size of n=352 (n=22 in each of 16 conditions) provides 80% power to detect an odds ratio of 2.0 (i.e., 20% vs. 33% tested). To account for attrition of up to 20% of enrolled participants, we propose a total sample size of 448 participants (n=28 in each of 16 conditions), ensuring complete data for at least n=22 per condition. Given the proposed sample size, when the main effect of an intervention component on a continuous measure of a secondary outcome or mediator is estimated in a linear model or independent-samples t-test, the sample size provides 80% power to detect a small standardized mean difference ($d = .30$). Moderator effects corresponding to an odds ratio of OR=1 in one subgroup and OR=4 in another can be detected with 83% power if subgroups sizes are roughly equal. To estimate the size of a mediated effect that can be detected given the proposed sample size, we use the approach described by Vittinghoff and colleagues¹⁴⁰ as implemented in PASS 2021. Given a substantial correlation between an intervention component and a hypothesized mediator ($r=.50$), an odds ratio of 1.50 can be detected with >80% power for the effect of a one-SD increase in a continuous mediator on the COVID-19 testing outcome, controlling for treatment assigned.

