15.5. Statistical methods

15.5.1. Quantitative data analysis

Intent-to-treat analysis will be our primary analytic approach and exploratory analyses will examine complier average effects of intervention components^{124,125}. Approaches to missing data will include full information maximum likelihood estimation¹²⁶ and multiple imputation¹²⁷. In sensitivity analysis, missing data will be treated as failure to achieve the desired outcome. If data are missing not at random (MNAR), we will employ sensitivity analysis, using selection¹²⁸ or pattern mixture^{129,130} models.

Aim 1: Identify which of four components or interactions between components contribute meaningfully to improvement in the primary outcome, COVID-19 testing with documentary evidence, and from these results, optimize a multicomponent intervention.

The primary outcome for Aim 1 is COVID-19 testing with documentary evidence by the final follow-up point (12-weeks post-baseline). Logistic regression will be used to estimate effects of components on the odds of COVID-19 testing. Intervention components will be effect-coded to estimate main effects, two-way, three-way, and four-way interactions of all four components (see **Equation 1**). The coefficient for an effect-coded main effect term (e.g., b_1), multiplied by two and exponentiated, will estimate the effect of the component (e.g., Component A) on the odds of testing. Similarly, the coefficient for an effect-coded interaction term, multiplied by two and exponentiated, will estimate interaction effects between or among components on the odds of testing. Similar logistic regression analyses will estimate effects of components on secondary outcomes.

Equation 1

Intervention optimization. Based on main and interactive effects estimated in Aim 1, we will use a decision-making process to select the most effective combination of component levels, eliminating ineffective or poorly performing components. The decision-making process will be led by Drs. [name], [name], [name], [name], and [name] and using procedures outlined in Collins⁴⁸. To identify

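### The analysis section gives secondary outcomes only logistic regression, while the power section relies on a linear model for continuous ones; the two conflict for vaccination attitudes

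*Combined protocol and SAP*

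**What the plan says.** **Analysis.** Section 15.5.1 (Aim 1) sets out a logistic model with the four components effect-coded and all interactions included. Each coefficient is doubled and exponentiated to give an effect on the odds of testing. Secondary outcomes then get one sentence: "Similar logistic regression analyses will estimate effects of components on secondary outcomes". No linear model, ordinal model, link function or cut-point is given for them.

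**Power.** Section 15.1 covers the case where a component main effect "on a continuous measure of a secondary outcome or mediator is estimated in a linear model or independent-samples t-test", and claims 80% power at d = 0.30.

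**Outcomes.** Sections 14.4 and 15.3 list "attitudes toward COVID-19 vaccination" among the secondary outcomes, and 14.4 applies it to all participants. The other outcomes listed there are in the main events or categories, such as test results, contact tracing, isolation and vaccine receipt.

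**Measurement.** Section 14.1.1 is headed "Domains in the assessment battery (BL and FU), Table 4". The attitude entry in that table carries citations but no item count, response format or scoring. Section 15.5.1 does not use a baseline attitude score as a covariate for this outcome. Baseline values enter only for mediators (Aim 2), and the moderator models add sociodemographics and occupation.

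**The concern.** The power section provides for a continuous secondary outcome and states the test on which its 80% rests. The analysis section names a different family of models for secondary outcomes. If vaccination attitudes is a score, the plan contains no analysis that matches its power statement.

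Two things are at stake. First, the analyst must decide later whether to split the score, where to split it, or whether to fit some other model, and that choice could be made after the data are seen. Second, some of the available choices have clearly less power than the plan reports for continuous outcomes. The plan also leaves unused a baseline measurement that it appears to collect and that would improve precision.

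**Working it through.** **Inputs**

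- Analysable sample, section 15.1: "a sample size of n=352 (n=22 in each of 16 conditions) provides 80% power to detect an odds ratio of 2.0". Each main effect uses everyone (section 9), so 352 / 2 = 176 per component level.
- Alpha 0.05, section 15.1. Sidedness is not stated; two-sided is assumed, and it reproduces the plan's figure.
- Effect d = 0.30 with SD 1, section 15.1.
- Assumed, not in the documents: a normally distributed score, and the baseline to follow-up correlation r.

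**Step 1. Reproduce the stated 80%.**
Power = Φ(d·√(n/2) − 1.96) = Φ(0.30 × √88 − 1.96) = Φ(2.814 − 1.96) = 80.4%. With the noncentral t it is 80.1%. The detectable difference at 80% power is (1.96 + 0.842) × √(2/176) = 0.299. With all 448 enrolled (224 per level) power would be 88.8%, so the statement rests on 352 completers and a linear model.

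**Step 2. Binary logistic regression on a split score.**
Shift a normal score by 0.30, cut it, and compare the two proportions with 176 per level.

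| Cut | Share above, lower vs higher level | Power | Loss from 80.4% (points) |
|---|---|---|---|
| Midway between the level means | Φ(−0.15) = 44.0% vs Φ(0.15) = 56.0% | 61.0% | 19.4 |
| 30% of lower level above | 30% vs 41.1% | 58.7% | 21.6 |
| 20% of lower level above | 20% vs 29.4% | 53.4% | 26.9 |
| About the top 20% of both levels together | 16.1% vs 24.5% | 50% | about 30 |
| 10% of lower level above | 10% vs 16.3% | 41.8% | 38.6 |

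First row worked: the difference is 0.119. The SE under the null is √(2 × 0.25/176) = 0.0533, and under the alternative √(2 × 0.44 × 0.56/176) = 0.0529. Power = Φ((0.119 − 1.96 × 0.0533)/0.0529) = Φ(0.28) = 61%.

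**Step 3. Check in the full factorial model.**
Simulation of the 16-term effect-coded model (22 per cell, 1,500 runs) gave 80.9% for least squares and 61.9% for logistic regression on a median split. Including the interaction terms does not change the picture.

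**Step 4. Ordinal logistic regression.**
A rank test, simulated as a proxy for a proportional-odds model, gave 78.8% with the score left continuous and 75.4% with five categories. Against about 80% that is a loss of roughly 2 to 5 points.

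**Step 5. Linear model with the baseline score.**
The residual SD becomes √(1 − r²), so power = Φ(2.814/√(1 − r²) − 1.96).

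- r = 0.3: Φ(2.950 − 1.96) = 83.9%
- r = 0.5: Φ(3.249 − 1.96) = 90.1% (89.5% in the simulation)
- r = 0.7: Φ(3.940 − 1.96) = 97.6%

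**The case against.** A reader might infer from Step 2 that the plan gives away about 20 points of power. The documents do not support that. They never mention splitting the score or a cut-point, and logistic regression does not require a binary outcome. An ordinal logistic model suits Likert-type data and costs little. The 20-point figure belongs to one unwritten choice, a binary split near the median.

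It can also be said that section 15.1 already names the linear model for continuous outcomes, and that most secondary outcomes are categorical. On that view the sentence in 15.5.1 is shorthand for the categorical ones, and the power claim, being conditional on a linear model, is not false. This is a plausible account of what was meant, but it does not settle the matter, because the analysis section is where the model must be specified. There the sentence follows directly on a binary odds model and refers back to it, with no ordinal or linear alternative. The same section's sensitivity analysis, which counts missing data as failure, also makes sense only for a binary outcome.

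Two further limits stand in full. Table 4 gives no scoring for the attitude measure, so treating it as a continuous scale is an inference. It is supported by section 15.1's provision for continuous secondary outcomes and by the nature of the construct. The table's heading also covers rows that cannot exist before randomisation, such as intervention acceptability and dose. It therefore suggests, but does not prove, that attitudes are measured at baseline.

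**Conclusion.** The inconsistency is real and limited in reach. For a continuous secondary outcome, the analysis in 15.5.1 and the power statement in 15.1 do not describe the same test, and vaccination attitudes is the outcome affected. The size of the consequence is conditional. At d = 0.30 with 352 completers, power is about 80% for the linear model, about 75% to 79% for an ordinal logistic model, about 61% for a near-median split, and about 50% to 53% for a cut near the top fifth. These figures assume a roughly normal score and a two-sided 5% test.

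It would go too far to say that the plan requires dichotomising, or that a given amount of power has been lost. The gain from baseline adjustment is a separate improvement. It depends on an assumed correlation and on the measure being taken at baseline. The primary analysis, the sample size and the rule for selecting components, which works on the odds of testing, are unaffected.

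**What to change.** Replace the secondary-outcome sentence in section 15.5.1 with text to this effect:

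*Binary secondary outcomes (for example, vaccine receipt) will be analysed by logistic regression on the effect-coded components. Continuous secondary outcomes (for example, the vaccination attitude score) will be analysed without dichotomising, by linear regression on the same effect-coded components, with the baseline value of the same measure as a covariate where it is collected at baseline. Twice the coefficient of a main effect estimates the mean difference between component levels.*

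Also state the items, response format and scoring of the attitude measure, and whether it is administered at baseline. If it is not, drop the covariate; the linear model still matches the 80% in section 15.1.

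The cost is a short amendment and a scoring definition. No new data collection is needed. Both should be fixed before the follow-up attitude data are examined.

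### Section 15.5.1 applies logistic regression of component effects to all secondary outcomes, but most of them exist only after a positive test and no analysis set is named

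*Combined protocol and SAP*

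**What the plan says.** Section 14.4, repeated in section 15.3, lists the secondary outcomes. One is the result of each test. Five are nested under the condition "If diagnosed with or has a positive COVID test result": confirmatory or repeat testing, contact tracing, self-isolation, care received and unintended consequences. Section 14.4 sets only two apart under the label "For all participants": attitudes toward vaccination and receipt of vaccination. Section 14.3 adds test completion as a further secondary outcome.

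The Aim 1 model in section 15.5.1 is a logistic regression: "Intervention components will be effect-coded to estimate main effects, two-way, three-way, and four-way interactions of all four components". The same paragraph ends: "Similar logistic regression analyses will estimate effects of components on secondary outcomes". The section opens with "Intent-to-treat analysis will be our primary analytic approach".

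For continuous measures, the power section (15.1) speaks differently: it covers the case where the effect on "a continuous measure of a secondary outcome or mediator is estimated in a linear model or independent-samples t-test".

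The documents give no analysis set for the positive-only outcomes, no coding rule for people who never tested or never tested positive, no minimum count, no descriptive fallback and no expected positivity.

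**The concern.** Whether a participant tests is what the components are meant to change. People who test, and people found positive, are therefore selected after randomisation by a process that may differ between component levels. Comparing self-isolation or contact tracing by component within that group does not compare the randomised groups, and it sits badly with the intent-to-treat principle in the same section. A component could appear to reduce isolation simply because it brought different people into testing.

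There is also a question of whether the model can be fitted at all. A full set of interactions among four two-level components needs data in all 16 conditions, while positives will be few.

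The missing-data text widens the gap. Section 15.5.1 plans maximum likelihood, multiple imputation and a sensitivity analysis that counts missing data as failure. Nothing separates an outcome that does not apply from one that is missing. An analyst could impute isolation for someone who was never positive, or count that person as having failed to isolate.

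**Working it through.** **1. The plan's own figure.** Section 15.1 assumes that participants at the off or lowest level "have a 20% chance of testing by the final follow-up", and targets an odds ratio of 2.0.
- Odds at 20% are 0.25; doubled, 0.50; the rate is 0.50/1.50 = 33.3%.
- The two-sided two-proportion formula at alpha .05 and 80% power gives 344 in total. With 176 per level (352), a Wald test on the log odds ratio has 80.1% power.
- 352/0.8 = 440, or 27.5 per condition; rounded up, 28 × 16 = 448.

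The stated 352 and 448 are reproduced.

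**2. Parameters.** Intercept 1 + main effects 4 + two-way 6 + three-way 4 + four-way 1 = 16.

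**3. Expected positives.** Positives = N × share tested × positivity. N and the shares tested come from section 15.1; 26.7% is the average of 20% and 33.3%. Positivity is assumed.

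| N | Share tested | Testers | 2% | 5% | 10% | 20% |
|---|---|---|---|---|---|---|
| 352 | 20% | 70.4 | 1.4 | 3.5 | 7.0 | 14.1 |
| 352 | 26.7% | 94.0 | 1.9 | 4.7 | 9.4 | 18.8 |
| 352 | 33.3% | 117.2 | 2.3 | 5.9 | 11.7 | 23.4 |
| 448 | 33.3% | 149.2 | 3.0 | 7.5 | 14.9 | 29.8 |

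**4. Can the model be fitted?** With all interactions, finite estimates need at least one yes and one no in each of 16 cells, so at least 2 × 16 = 32 positives. Below 16 positives some cells are empty and the parameters are not all identified. Every entry in the table is under 32.

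Reaching 32 is far from enough. In 20,000 simulated draws per count, with positives spread at random with equal probability over the cells and a 50% outcome rate, every cell held both outcomes in 0% of draws at up to 48 positives, 1.9% at 72 and 16.5% at 94.

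For test result among testers, each cell needs at least one positive. The chance of that was 0% with 18 positives, 0.5% with 24 and 14% with 36.

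**5. Would one main effect do better?** From a 50% base, 80% power for an odds ratio of 2.0 needs about 274 positives. With 24 positives the detectable odds ratio is about 45.

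**6. How large could selection bias be?** Illustration only; all values are assumed. Half the population is care-oriented. Isolation is 80% in that half and 40% in the other, positivity is equal, and the component has no effect on isolation. With the component off, 30% and 10% test (20% overall), so isolation among positives is (0.30 × 0.80 + 0.10 × 0.40)/0.40 = 70%.
- The component reaches only the less care-oriented half (30% and 36% test, 33% overall): (0.30 × 0.80 + 0.36 × 0.40)/0.66 = 58%. The spurious odds ratio is 0.60.
- The component doubles the odds of testing in both halves (46.2% and 18.2%): isolation is 68.7%. The spurious odds ratio is 0.94.

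The bias can be material or nearly absent, depending on who is drawn into testing.

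**The case against.** A reader might infer that the plan directs a full-interaction model fitted among positives. The documents do not say that. Section 15.5.1 says only that the analyses will be similar, which could allow a reduced model, and its intent-to-treat statement could point to coding everyone else as no. Sections 14.4 and 15.3 also say the outcomes will be examined in mixed-methods and integrated analyses, a use that needs no component-effect test. Test completion is a natural binary target for the sentence. All of this stands, and it narrows the point to an unspecified analysis set. It does not remove the point, because the plan states none of these choices, and test completion raises the same question of how non-testers are coded.

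A reader might also infer a known bias, such as an odds ratio of about 0.6. That is not supported: the figure depends on assumed selective uptake and shrinks to 0.94 under a uniform effect on testing.

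The count of positives is not a plan figure either. The 20% and 33% refer to documented testing, and undocumented positives may count toward these outcomes. But even if all 448 tested and 20% were positive (about 90), the full model would usually fail.

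On vaccination attitudes, section 15.1 already anticipates a linear model, so the conflict is between two sentences and not a settled choice of the wrong method. Baseline adjustment is a gain in precision, not the correction of an error.

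**Conclusion.** The concern holds as a gap in specification. Six of the eight outcomes listed in section 14.4 depend on having tested or on being diagnosed or positive, and the only analysis rule covering them names no analysis set and no exception. If the rule is applied among positives or testers, randomisation does not protect the comparison, by an amount and in a direction the documents cannot settle. Expected positives are about 2 to 19 at the average planned testing rate among 352 completers, and at most about 30 across the scenarios in the table, against 16 parameters and a minimum of 32 for finite estimates. These counts rest on an assumed positivity of 2% to 20% and on the testing rates in section 15.1.

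The primary outcome and the selection of components do not depend on these analyses, and section 15.1 claims no power for the positive-only outcomes. This is a low-to-moderate priority correction.

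**What to change.** In section 15.5.1:

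- Limit the logistic sentence to binary secondary outcomes defined for all randomised participants, such as receipt of vaccination. For test completion, state how non-testers are coded.
- Report test results and positive-only outcomes as counts and percentages by component level, without component-effect tests. State that these outcomes do not apply to people who never tested or were never positive, so that they are neither imputed nor counted as failures.
- If an all-randomised composite is also wanted, such as tested positive and self-isolated, fit main effects only with a penalised or exact method, and say that it largely reflects testing and infection. The full model would still fail: 18.8 positives with an assumed 70% isolating give about 13 events over 16 cells.
- For continuous vaccination attitudes, specify linear regression, in line with section 15.1, adjusted for the baseline score that the assessment battery (section 14.1.1, Table 4) already collects.

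The cost is SAP wording; no new data are needed. What is given up is component-effect estimates among positives, which the data could not support.

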Perceived susceptibility to, severity of COVID-19	Wong perceived susceptibility to (three items), and perceived severity of COVID-19 infection (three items) scales ¹⁰⁵
Perceived benefits of COVID-19 testing	Guidry 4-item Perceived Benefits of COVID testing ¹⁰⁶ ; $\alpha = 0.82$
Distrust and fear of COVID-19 testing	10-items assessed on a 5-point Likert-type scale drawn from existing reliable scales ¹⁰⁶⁻¹⁰⁸
Counter-narratives (conspiracy theories)	6-items assessed on a 5-point Likert-type scale drawn from existing reliable scales (e.g., I could be a guinea pig for a test with unknown consequences). ^{109,110}
Cognitive biases	Measurement of BE biases ⁴²
Behavioral Intentions	Various testing scenarios assessed with 3 items (e.g., I intend to get a COVID-19 test regularly) on a 6-item Likert scale ¹⁰⁶
Motivation/readiness	Importance of COVID testing and confidence in ability to get serial screening and tested as needed on a 1-100 scale. ¹¹¹
Social influences	
Perceived social norms	Adapting Latkin we will assess social norms using four items: injunctive (e.g., My co-workers encourage me to get a COVID test); descriptive (e.g., What percent of your co-workers do you think have gotten a COVID test) ¹¹² . $\alpha = 0.77$.
Altruism & collective responsibility	Three items on testing as an altruistic act (e.g., My getting tested helps my community reduce the spread of COVID) ¹⁰⁸
Structural influences	
Structural barriers to COVID-19 testing	Perceived barriers including poor access related to insufficient local sites, lack of paid sick leave, lack of childcare, language barriers ¹¹³
PRIMARY OUTCOME	
COVID-19 testing	COVID testing behavior (see protocol for definition)
SECONDARY OUTCOMES	
COVID-19 testing	Confirmatory and/or re-testing, contact tracing (by participant), self-isolation, health care, unintended consequences of testing
Vaccination	Testing behavior - CDE
	Vaccine Acceptance - CDE
	Attitudes toward COVID-19 vaccination ¹⁰⁶⁻¹⁰⁸ , receipt of vaccination doses
Intervention process domains	
Intervention acceptability	Client Satisfaction Questionnaire (YCSQ) –17 items; reliable and valid measure ¹¹⁴
Intervention social harms	Assessment of project-related social harms experienced in social and occupational domains.
Feasibility/Intervention dose	
Intervention dose	Number of assigned components attended, if assigned: number of peers educated, navigation contacts completed and their characteristics/content

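### Five secondary outcomes exist only for participants with COVID-19, yet 15.5.1 points them to the full component model: almost surely not estimable there, and any contrast among positives is not a randomised one

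*Combined protocol and SAP*

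**What the plan says.** Section 14.4 nests five outcomes under "If diagnosed with or has a positive COVID test result": confirmatory testing, contact tracing, self-isolation, health care receipt and unintended consequences. A separate list headed "For all participants" holds the vaccination outcomes, so the restriction looks deliberate. Section 15.3 nests the same five in the same way. Table 4 (section 14.1.1) words the group as "contact tracing (by participant), self-isolation, health care, unintended consequences of testing", with no limit to positives.

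For Aim 1, section 15.5.1 effect-codes the components to "estimate main effects, two-way, three-way, and four-way interactions of all four components". It then adds "Similar logistic regression analyses will estimate effects of components on secondary outcomes". It gives no reduced model, penalised method, minimum count or analysis population for the outcomes that apply only to positives. The same section states that "Intent-to-treat analysis will be our primary analytic approach".

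**The concern.** Two things do not fit together. First, few participants are likely to have a positive test, and a saturated logistic model in so small a group has no finite estimates. Second, having a positive test depends on having tested, which is what the components are designed to change. A comparison of component levels among positives is therefore a comparison of groups selected after randomisation, which sits badly with the intent-to-treat approach.

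Unintended consequences is the item where this matters most. Section 4.1.1 names fear of what follows a positive test, such as losing work or housing, as a barrier in this population. A component that leads more people to test could leave more of them affected while the contrast among positives shows nothing. With no analysis population stated, the denominator could also be chosen after the data are seen.

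**Working it through.** **1. The plan's own figure.** Inputs from 15.1: alpha 0.05 (two-sided assumed), 80% power, 20% tested at the lower level, odds ratio 2.0. The upper rate is 0.5/1.5 = 33.3%. Wald test of the log odds ratio, per level: (1.960 + 0.842)² × [1/(0.20 × 0.80) + 1/(0.333 × 0.667)] / (ln 2)² = 7.85 × (6.25 + 4.50) / 0.480 = 175.6. The total is 351.2, so 352, or 22 per condition. Attrition: 22/0.8 = 27.5, rounded up to 28; 28 × 16 = 448. The plan's figures reproduce, and its testing rates are used below.

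**2. Size of the model.** Intercept 1 + main effects 4 + two-way 6 + three-way 4 + four-way 1 = 16 terms over 16 conditions. The model is saturated. Finite maximum-likelihood estimates need at least one event and one non-event in every cell, so at least 16 × 2 = 32 positives. This bound needs no assumption about rates.

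**3. Likely number of positives.** Positives = N × share tested × positivity. The documents give no positivity, so the range is an assumption. The mean testing rate from 15.1 is (20% + 33.3%)/2 = 26.7%.

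| N | Tested | Positivity | Positives |
|---|---|---|---|
| 448 | 26.7% | 5 / 10 / 20% | 6.0 / 11.9 / 23.9 |
| 352 | 26.7% | 5 / 10 / 20% | 4.7 / 9.4 / 18.8 |
| 448 | 60% | 20% | 53.8 |
| 448 | 70% | 30% | 94.1 |

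**4. Chance that the 16-term model has finite estimates.** Simulation with positives spread at random over 16 equal cells:

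| Positives | Outcome frequency 20% | 30% | 50% |
|---|---|---|---|
| below 32 | 0 | 0 | 0 |
| 54 | 0% | 0.005% | 0.03% |
| 60 | 0% | 0.01% | 0.2% |
| 80 | 0.01% | 0.7% | 5% |
| 94 | 0.1% | 3% | 16% |
| 120 | 1.4% | 15% | 48% |

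**5. A main-effects model among positives (5 terms).** At outcome frequencies of 10%, 20% and 50%, the chance of finite estimates is about 1%, 5% and 14% with 10 positives; 13%, 49% and 88% with 20; and 50%, 91% and 100% with 40. Reducing the model helps estimability but leaves step 6 untouched.

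**6. Conditioning on testing.** Take 224 participants per level, testing at 20% v 33.3%, and assume 10% positivity and 30% risk per positive at both levels.
- Lower level: 224 × 0.20 × 0.10 × 0.30 = 1.34 people affected.
- Upper level: 224 × 0.333 × 0.10 × 0.30 = 2.24 people affected.
- The ratio is 0.333/0.20 = 1.67, while the odds ratio among positives is 1.0.

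If the added testers (13.3%) have half the positivity, the upper level gives 224 × (0.20 × 0.10 + 0.133 × 0.05) × 0.30 = 1.79, a ratio of 1.33. The odds ratio among positives is still 1.0.

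**7. Everyone as denominator.** With 28 per cell and event rate q, the chance that the saturated model is finite is (1 − q²⁸ − (1 − q)²⁸)¹⁶: about 0 at q = 2% and 1.3% at 5%. The 16-term model therefore does not suit this denominator either. A main-effect risk difference can be computed: for example, 4/176 v 2/176 gives +1.1 points (95% Newcombe score interval −2.1 to 4.7).

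**The case against.** The strongest reply is that 15.5.1 does not prescribe the 16-term model for these outcomes. Its phrase is a blanket one and cannot be literal for every item: attitudes toward vaccination is a scale, and 15.1 mentions linear models or t-tests for continuous secondary outcomes. That stands. The saturated model is the natural reading because no other is given, but it is an inference.

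Four stronger readings are tempting and are not supported.

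- A reader might infer that this is the trial's only measure of harm. It is not. Table 4 has a row for project-related social harms, 16.1.2 has social harms assessed at follow-up, and 16.6 schedules a structured social-impact interview at each follow-up, none limited to positives. Those items concern study participation rather than a COVID-19 test, and no analysis by component is stated, so they do not replace this outcome.
- A reader might infer that the model fails at any plausible count. That depends on assumed rates. The testing rates in 15.1 concern documented tests, half the sample receives kits, and the conditional group also includes people who are diagnosed. At 94 positives and 50% frequency the chance of finite estimates is 16%.
- A reader might take the ratio of 1.67 as general. It needs equal positivity among the added testers. In absolute terms the illustration is a gap of about one person.
- A reader might infer that participants without a positive test would be imputed or counted as failures, because "In sensitivity analysis, missing data will be treated as failure to achieve the desired outcome". That rule speaks of a desired outcome and does not fit a harm, and nothing in 15.5.1 treats an outcome that does not apply as missing.

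It is also fair to say that confirmatory testing, contact tracing and self-isolation are actions taken after a positive result. Counting them over everyone would mix uptake of testing with behaviour after diagnosis, so the all-participant measure is proposed only for unintended consequences.

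**Conclusion.** The point holds in a limited form. For the five outcomes restricted to diagnosed or positive participants, the analysis most naturally implied by 15.5.1 is impossible below 32 positives and almost surely not estimable up to about 60. The plan's own testing rates with an assumed 5-20% positivity give about 6 to 24. Separately from that assumption and from the choice of model, a component contrast among positives is not a randomised comparison. It can miss a rise in the number of people affected, by a ratio of 1.67 or 1.33 under the two sets of assumptions shown. Table 4 also differs from 14.4 and 15.3 on whom unintended consequences covers. This is a modest issue of secondary analysis: the primary testing result and the rule for selecting components stand as they are.

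**What to change.** In 15.5.1, exclude these five outcomes from the logistic models for secondary outcomes. Report them among diagnosed or positive participants as descriptive counts by component level, with no component model.

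For unintended consequences, also report the number affected out of all participants followed up, by level of each component, counting those not tested or not positive as no. Give a main-effect risk difference with a 95% score interval, labelled descriptive. Make the Table 4 wording agree with 14.4 and 15.3 on who is covered.

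The cost is a few sentences in the analysis section. The all-participant count uses the answers of diagnosed or positive participants and the number followed up, so it needs no new data collection. The downside is precision: as in the 4/176 v 2/176 example, the intervals will be wide and will not establish or exclude a difference between component levels.
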